7.2.6.1 Definitions

7.2.6.1.1 Adverse Events (AE)

According to ICH E2A,¹⁵ an AE is any untoward medical occurrence in a patient or a clinical investigation subject administered a pharmaceutical product and which does not necessarily have a causal relationship with this treatment. An AE can therefore be any unfavorable and unintended sign (including an abnormal laboratory finding), symptom, or disease temporally associated with the use

 GALDERMA	Title 43QMI902 Clinical Study Protocol - QM1114 - LCL and GL	Doc id MA-40371
--	---	----------------------------------

Effective date: 2020-06-09 07:02

Effective

Version: 4.0

of a medicinal (investigational) product, whether or not related to the medicinal (investigational) product.

Thus, any new sign, symptom or disease, or any clinically significant worsening of an existing sign, symptom or disease (including new episodes of a chronic disease [e.g., hay fever, allergy]) compared to the condition at the first visit, should be considered as an AE. Lack of efficacy is not considered as an AE.

Notes:

- There should be an attempt to report a diagnosis rather than the signs, symptoms or abnormal laboratory values associated with the report of an AE. However, a diagnosis should be reported only if, in the Investigator's judgment, it is relatively certain. Otherwise, symptoms, signs, or laboratory values should be used to describe the AE.
- Pregnancy is not to be considered as an AE; however, is an important medical event that must be monitored as described in Section [7.2.6.2.3](#).
- The effects of all BoNT products may spread from the area of injection to produce symptoms consistent with BoNT effects. These symptoms have been reported hours to weeks after injection. Remote spread of toxin that affects swallowing and breathing can be life threatening, and there have been reports of death. The risk of symptoms is increased in subjects who have underlying conditions (e.g. disorders of the neuromuscular junction) that would predispose them to these symptoms. BoNT is contraindicated in individuals with known hypersensitivity to any BoNT preparation or to any of the components in the formulation.

7.2.6.1.2 *Treatment Emergent Adverse Event (TEAE)*

A TEAE is an event that emerges during treatment, having been absent pre-treatment, or worsens relative to the pretreatment state.

7.2.6.1.3 *Serious Adverse Events (SAE)*

A SAE is any untoward medical occurrence that at any dose:

- Results in death,

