1.5.1 Adverse events

Adverse events (AEs) are to be monitored throughout the course of the study. All AEs reported will be coded using the Medical Dictionary for Regulatory Activities (MedDRA, version in force at the time of database freeze) and classified by MedDRA preferred term (PT) and system organ class (SOC). AEs will be defined as treatment-emergent adverse events (TEAEs) if the AE had an onset time greater than or equal to the time of study treatment. The study period for the purpose of AE collection is defined as the period from the signing of a study specific informed consent to study exit.

A two-point scale ("Yes" or "No" response) will be used for the causality assessments. The

 GALDERMA	Title 43QMI902 Statistical Analysis Plan US - QM1114-DP - GL&LCL	Doc id MA-43265
--	---	----------------------------------

Effective date: 2021-02-05 13:16

Effective

Version: 1.0

Treating Investigator should be asked to indicate a response to each of the following questions in the electronic Case Report Form (eCRF):

- “Do you consider that there is a reasonable possibility that the event may have been caused by the study product?”
- “Do you consider that there is a reasonable possibility that the event may have been caused by the study product injection procedure?”

If either of these questions is answered with a ‘Yes’, the AE will be considered related.

AE endpoints include incidence and severity of TEAEs.

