DP in LCL group), and then alphabetically if there are ties. Each subject will contribute at most one count per summarization category. In other words, if a subject has more than one TEAE with same PT, the subject will be counted only once for that PT. Similarly, if a subject has more than one TEAE for a SOC, the subject will be counted only once in that SOC and PT. For the event level analyses, the counts of each respective event will be presented. In general, percentages will be calculated using the number of subjects in the safety population for the denominator. For the subgroup analyses (described in [Section 2.5.2.1](#)) percentages will be calculated using the number of subjects in the safety population for each respective sub-category as the denominator.

For the “action taken” summary specifically, subjects will be only counted in ‘None’ category if no other action was taken. The onset/duration summaries will be presented at the event level (i.e. will include multiple AEs within the same SOC and PT). Number of days to onset and duration of event will be summarized by SOC and PT, using mean, SD, minimum, maximum, and median statistics. Time to onset will be calculated as the first day with the AE *minus* the Day 0. Duration will be calculated as the last day with the AE *minus* the first day with the AE *plus* one. The text below lists the imputation rules for partial/completely missing dates. Missing stop date will not be imputed and therefore no duration will be calculated in these cases. Instead, the number of AEs that were ongoing at the end of the study will be given.

Handling of Missing/Partial Dates

While every effort will be made to obtain full, complete information on every reported AE, the following imputation rules will be followed for any respective missing AE data:

For the purpose of calculating treatment emergence, onset time, and duration, the following date imputation rules will be used. Dates will be presented as is in the listings.

- Start Date
 - If start date is completely missing, it will be assumed that the AE started on the treatment date.
 - If the start date is missing the day, the first of the month will be used (i.e. UNK-JAN-2019 becomes 01-JAN-2019), provided the imputed date is on or after the subject’s treatment date; otherwise, the day of treatment will be used.

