 - If the start date is missing the month, the month of ‘June’ will be used (i.e. 01-UNK-2019 becomes 01-JUN-2019), provided the imputed date is on or after the subject’s treatment date; otherwise, the subsequent month after treatment will be used.
 - If the start date is missing the year, the year of treatment will be used (i.e. 01-JAN-UNK becomes 01-JAN-2019), provided the imputed date is on or after the subject’s treatment date; otherwise, the subsequent year after treatment will be used.
- End Date
 - If end date is completely missing, it will be assumed that the AE is still ongoing and will not be imputed.
 - If the end date is missing the day, the last of the month will be used (i.e. UNK-JAN-2019 becomes 31-JAN-2019)
 - If the end date is missing the month, the subsequent month after the start date will be used.

 GALDERMA	Title 43QMI902 Statistical Analysis Plan US - QMI114-DP - GL&LCL	Doc id MA-43265
--	---	----------------------------------

Effective date: 2021-02-05 13:16

Effective

Version: 1.0

- If the end date is missing the year, the year of treatment will be used (i.e. 01-JAN-UNK becomes 01-JAN-2019), provided the imputed date is after the start date; otherwise, the subsequent year after start date will be used.

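### For AEs with incomplete start dates, the SAP rules always give an onset on or after treatment and can give impossible values; separately, its TEAE definition omits the protocol's worsening criterion without declaring it

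*SAP*

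**What the plan says.** SAP 2.5.2 (Handling of Missing/Partial Dates) sets the AE start date as follows:

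- Completely missing: the treatment date.
- Day missing: the first of the known month if that is on or after treatment; "otherwise, the day of treatment will be used".
- Month missing: June if that is on or after treatment; "otherwise, the subsequent month after treatment will be used".
- Year missing: the treatment year if that is on or after treatment; "otherwise, the subsequent year after treatment will be used".

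The imputed dates determine treatment emergence, time to onset and duration. AEs that occur before treatment go to listings only. Such AEs are expected, because collection covers "the period from the signing of a study specific informed consent to study exit" (SAP 1.5.1) and screening may precede baseline by up to 14 days (Protocol 8.1.1).

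SAP 1.5.1 classes an AE as treatment-emergent "if the AE had an onset time greater than or equal to the time of study treatment". Protocol 7.2.6.1.2 is wider: "A TEAE is an event that emerges during treatment, having been absent pre-treatment, or worsens relative to the pretreatment state". SAP 2.8 presents Table 4 as the complete list of differences from the protocol's analyses, and its only entry concerns the per-protocol sensitivity analysis.

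**The concern.** A date rule for AEs may reasonably lean towards treatment emergence when the data leave the question open. These rules do so even when the recorded parts settle it: an event whose known month or known stop date precedes treatment is still moved onto the treatment date. The missing-month and missing-year rules also move onset later than the data require, past the recorded stop date or past study exit.

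Incidence and severity of TEAEs is a listed safety endpoint. Time to onset and duration of related AEs are tabulated with minimum and maximum (Tables 14.3.4 and 14.3.5), so a single duration of -25 days would show. Listing 16.2.7.4 (onset after 21 days) could also pick up events wrongly if it is selected on imputed onset.

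The definition raises a different problem, which does not depend on missing dates. An AE that starts in screening and worsens after injection is a TEAE under the protocol. If it is kept on one record, it is not a TEAE under the SAP.

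**Working it through.** **Inputs.** Time to onset = first AE day - Day 0, and duration = last AE day - first AE day + 1 (SAP 2.5.2). Screening is at most 14 days before Day 0 (Protocol 8.1.1). One month is 28 days and the Month 6 window is ±5 days (Protocol Table 2), so the window ends on day 6 × 28 + 5 = 173. The treatment and AE dates below are hypothetical.

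**The SAP's own examples.** Applied literally, the rules reproduce them: UNK-JAN-2019 gives 01-JAN-2019, 01-UNK-2019 gives 01-JUN-2019, and 01-JAN-UNK gives 01-JAN-2019. For a subject treated in 2019, the last holds only if treatment was on 01-JAN-2019 itself. With treatment on 02-JAN-2019 the rule returns 01-JAN-2020.

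**Test cases.**

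| Recorded start | Treated | Recorded stop | SAP start | Onset day | Duration (days) | What the known data allow |
|---|---|---|---|---|---|---|
| UNK-JUN-2020 | 06-JUL-2020 | 02-JUL-2020 | 06-JUL-2020 | 0 | 2 - 6 + 1 = -3 | June, before treatment |
| missing | 15-JUL-2020 | 10-JUL-2020 | 15-JUL-2020 | 0 | 10 - 15 + 1 = -4 | before treatment |
| 20-UNK-2020 | 15-JUL-2020 | 25-JUL-2020 | 20-AUG-2020 | 16 + 20 = 36 | -26 + 1 = -25 | 20-JUL: day 5, duration 6 |
| 10-UNK-2020 | 05-MAR-2020 | none | 10-JUN-2020 | 26 + 30 + 31 + 10 = 97 | – | 10-MAR (day 5) is the earliest |
| 20-UNK-2020 | 10-DEC-2019 | none | 20-JUN-2020 | 193 | – | no later than day 173 |
| 10-AUG-UNK | 15-AUG-2020 | none | 10-AUG-2021 | 365 - 5 = 360 | – | 10-AUG-2020, day -5 |

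In the fourth row, consent can be no earlier than 20-FEB-2020, so 10-FEB is excluded and the onset must follow treatment. In the last row, a window from day -14 to day 173 spans 187 days, less than a year. A known day and month can therefore fit only one year, and the rule replaces a date that could be deduced with an impossible one.

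**How general this is.** Each start-date branch returns the treatment date or later. Every pre-treatment AE with a missing day, month or year therefore becomes a TEAE, whatever the dates assumed. With a missing year, every such AE also lands after the end of the Month 6 window.

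Two further shares are illustrative only. They assume treatment dates uniform over 2020 and onsets uniform from day -14 to day 173:

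- Missing day: for treatment on days 1 to 14 of a month, 14 + 13 + … + 1 = 105 pre-treatment onsets fall in the previous month. The share is 12 × 105 / (366 × 14) = 1,260 / 5,124, or about 25% of pre-treatment onsets, in a month already known to precede the treatment month.
- Missing month: enumeration puts about 22% of post-treatment onsets beyond day 173.

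**TEAE definition.** The protocol has two limbs: new after treatment, or "or worsens relative to the pretreatment state". The SAP keeps the first limb and drops the second.

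**The case against.** The strongest defence is that the missing-day rule is an ordinary conservative convention. That stands when the partial date falls in the treatment month and no stop date precedes treatment. A known earlier month can arise only when treatment is in the first 14 days of a month, and screening and baseline may be on the same day. A reader might cite a February partial date with treatment on 20 March, but consent could not then be earlier than 6 March, so that onset lies outside the AE reporting period. The June/July case does not have this difficulty.

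Partial dates should also be few: subjects are asked about AEs at each visit, onset dates are recorded promptly, and the data pass logical and manual checks (Protocol 7.2.6.2.1 and 10.3). An event known to precede injection is unlikely to be judged related, so it would rarely reach the onset and duration tables. The date rules are the same in all arms, listings show dates as collected, and no efficacy result is touched. All of this limits the size of the problem. It does not justify prespecifying rules that return impossible values.

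On worsening, the protocol makes "any clinically significant worsening of an existing sign, symptom or disease" an AE in its own right (7.2.6.1.1), so a worsening entered as a new record has a post-injection onset and is counted. Nothing in the documents requires a new record, so the gap remains for worsening kept on the original one.

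**Conclusion.** The point holds for AEs with an incomplete start date: those events would be misclassified, or given a negative duration or a post-exit onset, in the circumstances shown. A reader might infer that the trial's TEAE counts, onset times and durations are wrong as a whole. The documents do not support that, because they give no frequency of partial dates and complete dates are untouched. Nor does the missing-day sentence produce onset after study exit; that comes only from the missing-month and missing-year rules.

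The TEAE definition is an undeclared departure from the protocol. It removes events from the tables only where a screening-onset AE that worsens after injection stays on one record. The two defects act in opposite directions: the date rules can add TEAEs and the definition can lose them. The net effect cannot be computed. Both should be corrected, because the rules are prespecified and correction is cheap. Day 173 as the end point assumes that the Month 6 window is kept.

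**What to change.** - **Start dates (SAP 2.5.2).** Restrict candidates to dates that match the known parts and lie between informed consent and the earlier of the recorded stop date and study exit. Among these, use the earliest date on or after treatment, which is the treatment date itself if it is a candidate. Classify the AE as pre-treatment only when every candidate precedes treatment. For a missing year, use the one year that falls inside the study window.
- **Why the consent limit is needed.** Simply taking the earliest date that matches the known parts would turn 10-UNK-2020, treated 05-MAR-2020, into 10-JAN-2020 and drop a true TEAE.
- **Check against the cases.** UNK-JUN-2020 and the completely missing start become pre-treatment. 20-UNK-2020, treated 15-JUL-2020, becomes day 5 with duration 25 - 20 + 1 = 6. 10-UNK-2020 becomes day 5. 10-AUG-UNK becomes 10-AUG-2020, pre-treatment, provided consent was given by then.
- **TEAE definition (SAP 1.5.1).** Add AEs with onset before treatment that worsen after it, as in Protocol 7.2.6.1.2.

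The cost is a few SAP sentences and a small change to the AE derivation program. Trial conduct and the efficacy analyses are unaffected.

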2.5.2.1 Subgroup analysis

To evaluate the consistency of the AE data, subgroup analyses will be performed. All TEAEs related to study product or injection procedure by SOC, PT, and maximum intensity will be repeated by the following subgroups. The same methods specified above ([Section 2.5.2](#)) will be followed

- Age (less than 65 years old, 65+ years old)
- Gender (Male, Female; if enough males are recruited)
- Prior botulinum toxin use (Naive, Non-Naive)
- Race (White, Black, Other)
- Fitzpatrick skin type (I-III, IV-VI)
- Site

2.5.2.2 Assessment of local/remote toxin spread and hypersensitivity

Any potential or suspected toxin spread or toxin hypersensitivity events will be evaluated separately. The same methods specified in Section 2.5.2 will be followed. Suspected toxin spread events and suspected hypersensitivity events will be summarized in separate tables. The investigator will conduct the investigation and evaluate if an AE is also a suspected toxin spread or hypersensitivity event; however, Appendix 7 in the CSP lists AEs potentially suggestive of spread of toxin.

2.5.3 Laboratory assessments

The laboratory data (hematology and clinical chemistry) at baseline Day 0 and Month 6 and the changes from baseline will be summarized by descriptive statistics. All clinically significant out-of-range laboratory values for blood samples collected at baseline will be recorded in the subject's medical history and all clinically significant out of range laboratory values for blood samples collected after baseline are to be reported as an AE if this abnormality was not present at the baseline visit or is assessed as having worsened since the baseline visit.

Throughout the study, it is possible that certain laboratory parameter results are below the limit of quantification (BLQ). Any BLQ laboratory values will be summarized by the imputed value of half the limit of quantification for that parameter.

All laboratory data will be presented in data listings as collected, without any imputations for BLQ values.

2.5.4 Neutralizing antibody testing

Sampling for antibody testing will be conducted at baseline Day 0, Month 1, and Month 6. For the antibody testing results, due to the timing and availability of the data, results will be presented in a separate report.

2.5.5 Physical examinations and vital signs

The number and percentage of subjects with normal/abnormal results in physical examination will be presented by visit and treatment. A shift table will be created to present any change from

	Title 43QMI1902 Statistical Analysis Plan US - QM1114-DP - GL&LCL	Doc id MA-43265
--	--	----------------------------------

baseline in normal/abnormal results in physical examination across the study visits for each treatment group.

Vital signs at baseline, Day 7, Day 14, Month 1 and Month 6, and the changes from baseline will be summarized by treatment and visit using descriptive statistics.

2.5.6 ECG

The aggregated value of each ECG measurement (described in [Section 1.5.6](#)) at baseline, Month 1, Month 6, and the changes from baseline will be summarized descriptively by treatment group at each visit. In addition, a shift table will be created to show any change from baseline to Month 6 in the overall ECG assessment.

QTcF and QTcB interval prolongation will be presented separately as well. The number and percentage of subjects with a QTcF and/or QTcB interval of >450 msec, >480 msec, and >500 msec will be summarized by treatment and visit, along with the number and percentage of subjects with a change from baseline in QTcF and/or QTcB interval of $30 - < 60$ msec and ≥ 60 msec.

2.5.7 Urine pregnancy test

A data listing will be provided to summarize the results of the urine pregnancy tests. All pregnancy SAEs will be flagged within the data listing.

2.6 Interim Analysis

Not applicable.

2.7 Determination of Sample Size

The sample size is determined by the number of subjects exposed to QM1114-DP in the LCL and GL, and amount of long-term safety data. Further, due to the public health emergency related to the COVID-19 pandemic during 2020, steps have been taken to ensure patient and practitioner safety in alignment with FDA Guidance dated May 11, 2020 (Guidance on Conduct of Clinical Trials of Medical Products during COVID-19 Public Health Emergency). Most notably, in partnership with clinical sites and the IRB, optional remote assessment procedures for efficacy and safety endpoints has been implemented to ensure safety and respect localized and elective restrictions. However, the number of subjects in the mITT population used in the assessment of the primary efficacy endpoint should still satisfy the sample size requirements for the primary efficacy analysis.

2.7.1 Historical data

During the study, the sample size was increased due to the public health emergency related to the COVID-19 pandemic to ensure a sufficient number of subjects in the mITT population. The study is planned to enroll approximately 413 subjects who will be treated with either:

- 60 units QM1114-DP (60 units in the LCL and placebo in the GL, 118 subjects),
- 50 units QM1114-DP (50 units in the GL and placebo in the LCL, 118 subjects),
- 110 units QM1114-DP (60 units in the LCL and 50 units in the GL, 118 subjects), or
- Placebo in both the LCL and GL (59 subjects).

 GALDERMA	Title 43QMI902 Statistical Analysis Plan US - QM1114-DP - GL&LCL	Doc id MA-43265
---	--	---------------------------

2021-02-05 13:16

Effective date:

Effective

Version: 1.0

No previous data on composite responder rates, with the same definition of composite responder as in the current study, is available for subjects treated with QM1114-DP in the LCL or GL, treated alone or in combination.

For the GL, previous phase 3 studies of BoNT used the same composite responder definition as in the current study, i.e. based on achievement of score 0 or 1 and at least 2 grades reduction from baseline as assessed by both investigator and subject concurrently on the 4-point evaluation scales.

CCI

CCI

CCI

2.7.3 Sample size calculation

The study is planned to include approximately 350 subjects in the mITT population: 100 subjects will be treated with QM1114-DP, 200 subjects will be treated with QM1114-DP and placebo, and 50 subjects will be treated with placebo.

The sample size is determined by the number of subjects exposed to QM1114-DP in the LCL and GL, and amount of long-term safety data.

2.8 Changes in Analysis Planned in the Protocol

The table below outlines all rationale and changes in the analyses specified in the SAP that differ from the analyses specified in the protocol.

Table 4 Changes in Analysis Planned in the Protocol

CSP Section	SAP section	Description/Rationale of Change
9.1.2.3	2.4.3.1	A sensitivity analysis of the primary efficacy endpoint will be performed based on the PP population regardless of meeting the criteria for PP population containing less than 90% of subjects in the mITT population, as was specified in the protocol.

 GALDERMA	<small>Title</small> 43QMI902 Statistical Analysis Plan US - QMI114-DP - GL&LCL	<small>Doc id</small> MA-43265
---	--	-----------------------------------

Effective date: 2021-02-05 13:16

Effective

Version: 1.0

3 Reference List

2021-02-05 13:16

Effective date:

Effective

Version: 1.0

4 Planned Tables and Figures

4.1 Statistical Tables

Table Number	Table Title	Analysis Population	(U)nique/ (R)epeat
